4. SUBJECT SELECTION

This study can fulfill its objectives only if appropriate subjects are enrolled. The following eligibility criteria are designed to select subjects for whom protocol treatment is considered appropriate. All relevant medical and non-medical conditions should be taken into consideration when deciding whether this protocol is suitable for a particular subject.

In order to achieve a reasonable distribution of subjects in the different weight categories, an enrollment target of no less than 20% will be set for both weight categories. Since weight and age are generally correlated, it is expected this will also lead to an acceptable distribution of subjects across the age range. Enrollment will be monitored to ensure that an appropriate distribution of age and weight is maintained.

Enrollment is competitive and enrollment at each site will depend on the capabilities of each site. The number of enrolled subjects is not pre-specified for any individual site.

4.1. Inclusion Criteria

Subject eligibility should be reviewed and documented by an appropriately qualified member of the investigator's study team before subjects are included in the study. A statement that the subject was eligible to enter the clinical trial should be completed by the investigator and included in the subject's source documentation.

There may be instances where siblings, or other subjects living in the same home or having the same caregiver, may both be eligible to enroll in the study.

There is an inherent risk of mis-dosing when more than one subject living in the same home is enrolled at the same time. This also includes subjects from separate households that have the same caregiver. In order to mitigate any risk with dosing, only one subject that shares a household/caregiver should be enrolled during any given timeframe. If another subject meets all inclusion/exclusion criteria for the study, that subject may also be enrolled if the enrollment periods do not overlap.

Subjects must meet all of the following inclusion criteria to be eligible for enrollment into the study:

1. Evidence of personally signed and dated informed consent document by the legal representative and an assent document by the subject indicating that the subject and a legal representative have been informed of all pertinent aspects of the study.
2. Subjects and their legal guardians who are willing and able to comply with scheduled visits, treatment plan, laboratory tests, and other study procedures.
3. In-patient and/or out-patient male and female subjects aged 10-17 (inclusive) at screening.
4. Primary diagnosis of Bipolar I Disorder (current or most recent episode manic), as defined by DSM-V criteria and confirmed by the Schedule for Affective Disorders and Schizophrenia for School Age Children (K-SADS). Current symptoms supporting the diagnosis must have been present for at least 7 days prior to screening.
5. YMRS score ≥ 17 at the screening and baseline visits.
6. In the investigator's opinion, the subject must be likely to benefit from therapy with an atypical antipsychotic drug.
7. Body Mass Index (BMI) z-score between -1.65 and +2.00, inclusive.
8. Subject must be willing and able to discontinue any medications that are prohibited in this study. Any such medications must be discontinued (according to the timeframes in [Section 5.5](#)) prior to baseline.

Subjects who are receiving prohibited medications are to be considered for the protocol only if discontinuation of the medication does not compromise the welfare of the subject and/or alternative medication that is allowed by the protocol is available and appropriate for the subject.

Psychotropic medications should be tapered down per accepted medical practice and the specific package insert instead of being abruptly discontinued.

If psychotherapy has been ongoing for 3 months prior to the screening visit, it can be continued during the study provided there is no increase in the frequency or duration of the psychotherapy or change in the type of psychotherapy being provided.

9. All male and female subjects who are sexually active and/or their legal guardians, as appropriate, must agree that a highly effective method of contraception be used throughout the study and for 28 days after the last dose of assigned treatment.

4.2. Exclusion Criteria

Subjects presenting with any of the following will not be included in the study:

1. Subjects who are investigational site staff members directly involved in the conduct of the trial and their family members, site staff members otherwise supervised by the Investigator, or subjects who are Pfizer employees directly involved in the conduct of the trial.
2. Subjects who are clinically stable on treatment regimens that are being well tolerated.
3. Subjects with substance-induced psychotic disorder or whose behavioral disturbance is thought to be due to substance abuse.
4. Subjects with DSM-V defined Substance Use Disorder (including psychoactive substance or alcohol use disorders) within the preceding 1 month of screening (does not apply to nicotine or caffeine).
5. Subjects who are judged by the investigator as being at imminent risk of suicide.
6. Subjects who are judged by the investigator as being at imminent risk of homicide.
7. Subjects should be excluded or a risk assessment should be done to verify that it is safe for the subject to participate in the trial if the subject's responses on any of the screening instruments or other screening information based on the investigator's judgment indicate:
 - A suicide ideation associated with actual intent and a method or plan at any time in their lifetime such that a positive response ('Yes') is made on items 4 or 5 of the suicidal ideation subscale of the C-SSRS;
 - Any lifetime history of suicide behaviors such that a determination of 'yes' is made to any of the suicide behavior items of the C-SSRS. Subjects with significant Intellectual Disability (ie, Intelligence Quotient (IQ) <70) that would interfere with study conduct or with the interpretation of the study assessments.
8. Subjects with significant Intellectual Disability (ie, Intelligence Quotient (IQ) <70) that would interfere with study conduct or with the interpretation of the study assessments.

9. Subjects with Autism Spectrum Disorder (including autistic disorder, Rett syndrome, childhood disintegrative disorder, pervasive developmental disorder – not otherwise specified (PDD-NOS), Asperger syndrome).
10. Subjects with Disruptive Mood Dysregulation Disorder.
11. Subjects with schizophrenia, schizoaffective disorder, schizophreniform disorder, or delusional disorder.
12. Other severe acute or chronic medical or psychiatric condition or laboratory abnormality that may increase the risk associated with study participation or investigational product administration or may interfere with the interpretation of study results and, in the judgment of the investigator, would make the subject inappropriate for entry into this study.
13. Subjects with controlled or uncontrolled Type 1 diabetes.
14. Subjects with Type 2 diabetes unless diagnosed ≥ 6 months prior to screening and on a stable, well controlled treatment regimen (ie, diet and/or oral hypoglycemic agents; insulin use is considered exclusionary).
15. Subjects with a history of seizure or epilepsy.
Subjects with a history of febrile seizures are eligible if no seizures have occurred during the last 3 years.
16. Subjects with a history of syncopal episodes (sudden loss of consciousness with loss of postural tone and not preceded by a pre-syncopal phase) or unexplained loss of consciousness.
Subjects with a history of occasional syncopes of probable vasovagal origin (onset not sudden but preceded by a pre-syncopal phase, presence of predisposing factors such as blood sampling procedure, standing, hot shower, hair curling, etc) are eligible.
17. Subjects with any medical condition or dietary habit that has a significant potential to alter the absorption of the study drug; or subjects taking any medication that may alter drug absorption (eg, anorexia nervosa, bulimia, chronic use of laxatives).
18. Subjects with uncorrected hypothyroidism or hyperthyroidism or whose thyroid function and medication regimen have been stable less than 1 month prior to screening.
19. Alanine aminotransferase (ALT)/Aspartate aminotransferase (AST) values $\geq 2x$ and total bilirubin values $\geq 1.5x$ the upper limits of normal.

Subjects with an isolated increase of unconjugated bilirubin (Gilbert's syndrome) are eligible.

20. Subjects with a history of chronic hepatitis, known serologic evidence of acute hepatitis or chronic hepatitis (positive hepatitis B virus surface antigen (HbsAg)), or subjects with known hepatitis C antibodies and elevated LFTs.
21. Subjects known to be Human Immunodeficiency Virus (HIV) positive.
22. Subjects with clinically significant hypokalemia or hypomagnesemia not corrected and stabilized by the addition of dietary supplements or some other corrective measure prior to baseline.
23. Subjects with a history of significant cardiovascular disease, including conditions that have previously required treatment or acute evaluation, or significant concurrent cardiovascular disease, including hypotension, congestive heart failure, or congenital heart disease.

Non-clinically significant sinus bradycardia or sinus tachycardia will not be considered significant medical illnesses and would not exclude a subject from the study.

Isolated atrial septal defect (ASD), ventricular septal defect (VSD, or patent ductus arteriosus (PDA) will not be considered significant medical illnesses if they are surgically corrected.

24. Subjects with a history of cardiac arrhythmias, conduction abnormalities or known personal history of QT prolongation (including congenital long QT syndrome).
25. Subjects with a known genetic risk for prolonged QT syndrome.
26. Subjects with a clinically significant ECG abnormality at screening or baseline.
27. Subjects with a QTc (Fridericia) ≥ 450 msec at screening or baseline, which is still prolonged on repeat ECG.
28. Subjects taking any medications that are prohibited (see [Section 5.5](#)).
29. Subjects who are taking or have previously received clozapine.
30. Use of a depot antipsychotic within 4 weeks, or a monoamine oxidase inhibitor, Abilify[®] (aripiprazole) or Prozac[®] (fluoxetine) within 2 weeks prior to baseline.
31. Subjects known by medical history or hospitalization records to have used phencyclidine within the 30 days prior to screening.
32. Subjects requiring treatment with drugs which have been consistently observed to prolong the QT interval (see [Section 5.5](#)).

33. Subjects with history of antipsychotic-induced EPS that does not respond to anti-parkinsonian medication.
34. Subjects with a prior episode of neuroleptic malignant syndrome or prior hypersensitivity to antipsychotic agents.
35. Subjects known to be allergic to ziprasidone.
36. Subjects with a history of non-responsiveness to ziprasidone after an adequate treatment period at a dose between 40-80 mg daily for subjects weighing <45 kg and 120-160 mg daily for subjects weighing \geq 45 kg.
37. Subjects currently receiving ziprasidone 30 days prior to screening.
38. Participation in other studies involving investigational drug(s) (Phase 1-4) within 30 days before the current study begins and/or during study participation.
39. Pregnant females; breastfeeding females; males and females who are sexually active who are not using highly effective contraception or not agreeing to continue highly effective contraception for 28 days after last dose of assigned treatment.
40. Subjects that have had unprotected sex within the last 2 weeks prior to screening and do not have 2 negative pregnancy tests two weeks apart are not eligible to receive study drug.
41. Siblings, or other subjects living in the same home or having the same caregiver during the same enrollment period.

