5.1. ITT Analysis Set

For this protocol, an intent-to-treat (ITT) analysis set will be defined as the set of all patients who were randomized, had baseline measurements, took at least 1 dose of study medication (Ziprasidone or placebo), and with at least 1 post-baseline visit. This definition of ITT may be considered a modified ITT definition; however, it will be referred to as ITT throughout the protocol and the SAP.

5.2. ‘Per Protocol’ Analysis Set

The per-protocol (PP) analysis set will include all patients in the ITT set without major protocol violations considered to impact the interpretation of the primary efficacy endpoint. Protocol deviations will be reviewed to generate the list of subjects with significant deviations to be excluded from the PP analysis set. The PP exclusion criteria will be finalized prior to breaking the blind.

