5.5.2. Deviations Assessed Post-Randomization

Protocol deviations include but are not limited to the following:

- Violations on concomitant medications (See protocol section 5.5);
- Lack of compliance (level to be defined case by case);
- Dosing errors (eg, treatment misallocation, overdose/under-dose).

A full list of protocol deviations will be compiled for the study report prior to database closure. All deviations will be reviewed, and a determination made for the handling of each case. This review will be documented in a note to the study file prior to un-blinding the study database.

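### Exclusion criterion 19 joins its ALT/AST and bilirubin limits with 'and'; read literally, neither limit excludes on its own (minor wording defect)

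*Protocol*

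**What the plan says.** Criterion 19 in Protocol 4.2 names ALT/AST and total bilirubin, gives each its own multiple of ULN (2 and 1.5), and joins the two with *and*: "values $\geq 2x$ and total bilirubin values". A second sentence follows: "Subjects with an isolated increase of unconjugated bilirubin (Gilbert's syndrome) are eligible".

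The opening line of 4.2 makes any one numbered entry enough to exclude. It does not say how two conditions inside one entry combine.

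Two neighbouring criteria also bear on the liver:

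- Criterion 12 covers other severe conditions and laboratory abnormalities. It has no number and applies where the finding, "in the judgment of the investigator, would make the subject inappropriate for entry into this study".
- Criterion 20 covers hepatitis. Its last clause reads "or subjects with known hepatitis C antibodies and elevated LFTs", with no numeric limit.

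Protocol 8.6.2 has numeric ALT/AST thresholds, but they identify possible drug-induced liver injury on study. They are not entry limits.

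**The concern.** A numeric laboratory exclusion exists so that every site takes the same decision on the same result. Criterion 19 supports two opposite decisions for two kinds of child: one whose ALT or AST is at or above 2 times ULN with bilirubin below its limit, and one whose bilirubin is at or above 1.5 times ULN, is not Gilbert's, and comes with enzymes below their limit. On the literal wording both pass criterion 19. If the two limits are separate, both are excluded.

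What is at stake is safety at entry and consistency between sites in a placebo-controlled paediatric trial planned for about 60 to 70 sites. The efficacy inference is not at stake.

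**Working it through.** The plan gives no figure to reproduce, so the check is one of logic and of wording.

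**Inputs (criterion 19, Protocol 4.2).** Let A mean ALT or AST at least 2 times ULN (taking the slash as either enzyme), and B mean total bilirubin at least 1.5 times ULN. Let G mean that B holds only as an isolated unconjugated rise (Gilbert's).

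**Rules compared.** Literal: exclude if A and B. Alternative: exclude if A or B. Each is tested without and with the Gilbert's sentence.

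| Profile | Literal *and*, no Gilbert's sentence | Literal *and*, with it | *Or*, no Gilbert's sentence | *Or*, with it |
|---|---|---|---|---|
| 1. Neither A nor B | passes | passes | passes | passes |
| 2. B only, not G | passes | passes | excluded | excluded |
| 3. B only, G | passes | passes | excluded | passes |
| 4. A only | passes | passes | excluded | excluded |
| 5. A and B | excluded | excluded | excluded | excluded |

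**Results.**

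- Under literal *and*, the Gilbert's sentence changes 0 of 5 profiles. An isolated bilirubin rise means A is false, so the joint condition is never met. Under *or*, the sentence changes 1 profile (profile 3).
- With the sentence applied, the two readings disagree on 2 profiles, 2 and 4. For example, ALT at 5 times ULN with normal bilirubin passes criterion 19 read literally and fails it under *or*.
- These are counts of logical cases and say nothing about how often each occurs.

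**Wording elsewhere, for *or*.** Sentences attached to other criteria re-admit subjects whom the rule would otherwise catch. Criterion 15 excludes a seizure history and then says "Subjects with a history of febrile seizures are eligible if no seizures have occurred during the last 3 years". Criterion 23 excludes significant cardiovascular disease, including congenital heart disease, and then says that certain isolated defects "will not be considered significant medical illnesses if they are surgically corrected". The Gilbert's sentence fits this pattern only under *or*. Section 8.6.2 also uses an explicit term for concurrence when it requires both an enzyme and a bilirubin abnormality.

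**Wording elsewhere, for literal *and*.** Criterion 20 uses *and* to require both hepatitis C antibodies and raised liver tests. Criterion 40 requires unprotected sex and the lack of two negative tests together. Criterion 22 uses *or* where either low potassium or low magnesium is enough.

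The list therefore points both ways. The redundancy makes *or* the likelier intention, but a careful site could still apply the literal text.

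**Other numeric gates.** None was found among the entry criteria. Criterion 12 is discretionary, criterion 20 is limited to hepatitis, and 8.6.2 applies on study.

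**The case against.** The strongest reply is that context already settles the matter. Any single entry in the list excludes, each analyte has its own threshold, and the Gilbert's sentence makes sense only if bilirubin alone can exclude. Nothing in the documents shows a site reading it otherwise. This stands in part: the two-limit reading is open to sites and many may use it. It does not remove the defect, because the text still has to be read against its own connector, and criterion 20 uses the same connector conjunctively.

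A second reply is that the Gilbert's sentence could be useful even under literal *and*, by telling investigators not to use criterion 12 against such subjects. That is fair, so the redundancy claim is confined to criterion 19. Redundancy is also imperfect evidence of error here: the vasovagal sentence in criterion 16 and the sinus-rhythm sentence in criterion 23 only clarify.

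A third reply concerns safeguards. A reader might infer that children with marked enzyme rises could enter unchecked. The documents do not support that. Protocol 7.2.1 requires the investigator to mark each out-of-range value as clinically significant or not. Protocol 6.2 allows time for laboratory results to be received and repeated before eligibility is confirmed, and repeats chemistry at baseline if screening was clinically significantly abnormal. Chemistry is drawn again at Day 8 (6.3.1). These steps give structure to the criterion 12 judgment. They do not supply a numeric limit. Nor does 8.6.2, which provides for subjects whose enzymes were already raised at baseline: its enzyme threshold for them moves with the baseline value (at 3 times ULN it is 2 x 3 = 6 times ULN).

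**Conclusion.** The point holds as a minor wording defect. As written, criterion 19 excludes only the combination of both elevations and sets no numeric cap on an isolated ALT/AST rise or on an isolated bilirubin rise that is not Gilbert's. Its Gilbert's sentence is then redundant within the criterion. That *or* was meant is a well-supported inference, but the documents do not state it.

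The size cannot be calculated. The documents give no frequency for either kind of subject, so any expected count would only restate an assumed rate. The number is probably small, given a general paediatric psychiatric population and investigator review of every abnormal value.

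Two further inferences should be resisted. The first is that the defect threatens the efficacy result. It does not: power, alpha and the primary ITT analysis do not depend on criterion 19, and the per-protocol set in SAP 5.2 keeps subjects "without major protocol violations considered to impact the interpretation of the primary efficacy endpoint", so little change is expected there either. The second is that subjects already enrolled with an isolated elevation are protocol deviators. SAP 5.5.1 ties that label to entry criteria not being properly satisfied, and a child who met the literal text arguably did satisfy them. The case-by-case review in SAP 5.5.2 ("All deviations will be reviewed, and a determination made for the handling of each case") does not justify applying a corrected rule retrospectively.

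**What to change.** Reword criterion 19 to exclude ALT or AST at least 2 times ULN, or total bilirubin at least 1.5 times ULN, and leave the Gilbert's sentence as it is. This settles the connector and the slash between the enzymes, and gives the Gilbert's sentence a function.

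Issue the change prospectively, bundled with the next amendment or clarification. The text change is a few words. The cost lies in the IRB/IEC approval required by Protocol 12.1 and in notifying about 60 to 70 sites. The downside is that a few more subjects may be excluded at screening.

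SAP 2.2.1 refers to a subject evaluability meeting already held, so enrolment may be complete. If so, the amendment serves no purpose for this trial. At most, list the subjects enrolled with an isolated elevation, for information, without classing them as deviators or changing any analysis set.

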4.3. Randomization Criteria

At the baseline visit, subjects must continue to meet all inclusion and exclusion criteria in order to qualify for randomization.

4.4. Life Style Guidelines

All male and female subjects who, in the opinion of the investigator, are biologically capable of having children and are sexually active, must agree to use a highly effective method of contraception consistently and correctly for the duration of the active treatment period and for at least 28 days after the last dose of investigational product. Subjects who are not sexually active (are abstinent) will not be required to use contraception. The investigator, in consultation with the subject, will select the most appropriate method of contraception for the individual subject from the permitted list of contraception methods, and instruct the subject in its consistent and correct use. The investigator, at each study visit, will confirm and document consistent and correct use. In addition, the investigator will instruct the subject to call immediately if the selected birth control method is discontinued or if pregnancy is known or suspected.

To improve compliance with contraception, the investigator should, as permitted by local law, provide: (a) confidential contraception counseling and (b) assistance accessing additional reproductive services, if needed.

Highly effective methods of contraception are those that, alone or in combination, result in a failure rate of less than 1% per year when used consistently and correctly (ie, perfect use) and include:

1. Established use of oral, inserted, injected or implanted hormonal methods of contraception are allowed provided the subject remains on the same treatment throughout the entire study and has been using that hormonal contraceptive for an adequate period of time to ensure effectiveness.
2. Correctly placed copper containing intrauterine device (IUD).
3. Male condom or female condom used WITH a spermicide (ie, foam, gel, film, cream, suppository).
4. Male sterilization with appropriately confirmed absence of sperm in the post-vasectomy ejaculate.
5. Bilateral tubal ligation or bilateral salpingectomy.

